8.1 Recording of Adverse Events

Numerous complications or sequelae of hip fracture surgery are outcomes for the study. Only adverse events that are related to the study treatment itself will be considered study adverse events.

At each contact with the subject, clinical personnel will seek information on adverse events by specific questioning and, as appropriate, by examination. This information will be recorded in the electronic medical record. The research coordinator will review and abstract this information into the study database, which will provide systematic recording and classification of a specific list of potential adverse events.

The clinical course of each event will be followed until resolution, stabilization, or until it has been determined that the study intervention or participation is not the cause. Serious adverse events that are still ongoing at the end of the study period will be followed up to determine the final outcome.

8.2 Relationship of AE to Study

The PI will determine, in his judgment, the relationship of each adverse event to the study procedures should be characterized. The relationship will be classified as probably related, possibly related, or unlikely to be related.

8.3 Reporting of Adverse Events and Unanticipated Problems

Unanticipated problems, as defined by HRPP policy, will be reported to the IRB in accordance with the same policy. All other adverse events, withdrawals, and study deviations will be reported in summary form during the continuing IRB review of the study or in the final report.

9 Data Management and Record Keeping

9.1 Database and Data Management

The study database will be designed and maintained in REDCap, a HIPAA compliant database (Harris et al). Study staff will be granted access to database sections based upon role. Only the pharmacists responsible for randomization will have access to the un-blinded study group assignment assigned by and recorded within REDCap. Research staff will have access to enter data but not extract summary data. Clinical personnel will not have any access to the study database to maintain equipoise and independence. Subject identifiers will be maintained in the database to facilitate the conduct of the study and insure accurate data collection. Upon completion of the study, the database will be locked and subject identifiers will be secured and not connected with the study data. Study data will be maintained in REDCap after completion of the study in archive mode.

The study screening log of patients who are not enrolled in the study will also be maintained in REDCap. The log will not contain any personal identifiers for these patients.

9.2 Records Retention

Study records will be retained for a minimum of 6 years, in accordance with HRPP policy.

10 Study Monitoring

10.1 Quality Assurance Monitoring

The study PI is responsible for ensuring the ongoing quality and integrity of the research study. However, as an investigator-initiated study without an external monitor that conducts monitoring, the TAHFT study will be prioritized for monitoring by the Research Quality Assurance Office of the LG HRPP. Compliance with HRPP policies will be assessed, consent forms will be reviewed, and IRB correspondence and any other regulatory documentation will be checked. Study data may be sampled to be checked for accuracy.

Should any concerns about non-compliance emerge, HRPP policy for review and investigation will be followed.

10.2 Data and Safety Monitoring

The Data and Safety Monitoring Committee (DSMC) for TAHFT comprises four individuals who work at LGH. Because the drug is an approved drug and there is significant experience with its use, it is believed that an internal committee can adequately monitor the trial. The committee will include a trauma surgeon, anesthesiologist, orthopedic surgeon, and orthopedic nurse, as well as a biostatistician. In addition, the principal investigator, [name], will attend committee meetings to address protocol. As the principal investigator, he is the person most familiar with the drug protocol and in the best position to address questions about it. However, he will not participate in any votes about study continuation or termination.

The first meeting of the committee will take place once the 50 subjects have been enrolled or after 6 months, whichever occurs first. Thereafter, the committee will meet biannually to review accumulated safety data and as hoc as needed to review or address any adverse events. The principal investigator will be aware of all adverse events that may occur in the study and will be responsible to call ad hoc meetings of the DSMC if necessary. Specific safety outcomes to be monitored include:

- Rate of 30 day readmissions and reason
- Complications within 90 days from surgery
- Other unanticipated events

One interim analysis will be conducted when 75% of enrollment is achieved to determine if the study should stop early for efficacy or futility. It also will allow assessment of the benefits concordantly with the risks.

11 Ethical Considerations

The study will not begin until it has received approval from the LGH Institutional Review Board (IRB). Any changes to the protocol or consent form that represent potential changes to the risk-benefit ratio or an increase in what is required of subjects will be submitted to the IRB as an amendment for review before it is implemented (unless a delay in implementation would compromise subject safety).

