As a secondary outcome, daily hemoglobin and hematocrit levels will be assessed using a mixed-effects linear model with adjustment for appropriate covariates. Safety/complication outcomes such as 30-day readmissions, embolic events or other complications will be assessed using appropriate binary or Poisson models. Descriptive statistics using appropriate comparative models will be used to assess homogeneity of demographics and any differences in outcomes between the control and intervention groups.

One interim analysis is planned to assess the primary endpoint for significant efficacy sufficient to stop the trial early. The interim analysis is planned for the $\frac{3}{4}$ point of the trial or a minimum of 300 subjects enrolled. To compensate for one interim and one final analysis, we will employ the O'Brien-Fleming adjustments to significance level criteria with $p < 0.0054$ for the interim analysis and $p < 0.0492$ for the final analysis. Based upon a simulation of our primary outcome, futility will be reached at the interim analysis point if the control group has a 30 (30/150 = 20%) or fewer subjects that have experienced a transfusion and the intervention group has 26 (26/150 = 17.3%) or more subjects that have experienced a transfusion. Even if the remaining 50 intervention subjects to be enrolled experience no transfusions and the transfusion rate remains at 20% in the control group, H_0 will not be rejected.

Futility Boundary Based Upon Control Group Transfusion Rate and Projected Intervention Group Number Transfused

8 Safety and Event Reporting

The study will comply with requirements of the Lancaster General Human Research Protection Program (HRPP) policies regarding reporting of unanticipated problems and adverse events.

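### Section 10.2 has the principal investigator attend monitoring committee meetings with only his vote withheld, so he could learn interim results by arm while up to 100 of 400 subjects are still to be enrolled.

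*Combined protocol and SAP*

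**What the plan says.** Section 10.2 (Data and Safety Monitoring) says that the principal investigator "will attend committee meetings to address protocol", on the ground that he knows the drug protocol best. The one restriction is that "he will not participate in any votes about study continuation or termination". The section describes no open and closed sessions, no recusal when results by arm are shown, and no rule on who receives the interim report.

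The same section places the interim analysis with this committee: "One interim analysis will be conducted when 75% of enrollment is achieved to determine if the study should stop early for efficacy or futility". It adds: "It also will allow assessment of the benefits concordantly with the risks".

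Section 7.2 sets the timing at the three-quarter point or "a minimum of 300 subjects enrolled". The efficacy threshold is p < 0.0054 at the interim and p < 0.0492 at the end. Futility is declared if the control group has 30 of 150 or fewer transfused and "the intervention group has 26 (26/150 = 17.3%) or more subjects that have experienced a transfusion".

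Section 5.6 keeps everyone but the study pharmacists blinded to treatment assignment. Section 9.1 restricts the assignments to the randomizing pharmacists, stops research staff from extracting summary data, and keeps clinical personnel out of the database so that equipoise and independence are preserved.

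**The concern.** Withholding a vote does not withhold information. Both interim rules compare the arms, so whoever sits through their application sees the direction and size of the difference. If the trial then continues, the person leading it could hold that knowledge while enrolment is open at its only site.

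At stake are equipoise, the pace and selection of enrolment, and transfusion practice across both arms. A change in any of these could shift event rates or power in the last part of the trial. The principal investigator also judges the relatedness of each adverse event (section 8.2) and can call ad hoc committee meetings (section 10.2). The protections in sections 5.6 and 9.1 show that the plan values independence, but they cover assignments and the database. They do not cover what is presented at a committee meeting.

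**Working it through.** **1. Do the interim rules need data by arm?** Yes. The efficacy rule is a p-value for an odds ratio between arms, and the futility rule is written as one count per arm. Neither can be applied to pooled data.

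**2. How many subjects remain?** Planned enrolment is 400 (section 4.1) and the interim needs at least 300 (section 7.2).
- 400 − 300 = 100, which is 25%. Because 300 is a minimum, 100 is an upper bound.
- Enrolment over 24 months, taken as even: 400/24 = 16.7 per month, so 100/16.7 = 6 months.
- No pause for the analysis is stated. If enrolment runs on for k months (assumed), 100 − 16.7k remain: 83, 67 or 50 for k = 1, 2 or 3.

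**3. Would the expected result stop the trial?** Section 7.1 assumes 20% against 10%, which is 30/150 against 15/150 at the interim. The likelihood ratio statistic is G = 2 Σ O ln(O/E), with expected counts of 22.5 transfused and 127.5 not transfused in each arm:

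G = 2[30 ln(30/22.5) + 15 ln(15/22.5) + 120 ln(120/127.5) + 135 ln(135/127.5)] = 5.98, p = 0.0145 on 1 df.

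This misses 0.0054. With 30 control events, 14 in the tranexamic acid arm also misses (p = 0.0084), and 13 is needed (p = 0.0046).

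**4. How the futility rule was read.** The figure titled "Futility Boundary Based Upon Control Group Transfusion Rate and Projected Intervention Group Number Transfused" is not shown in the text available, so two readings were used.
- *Reading A:* only the stated cell, control ≤ 30 and intervention ≥ 26.
- *Reading B:* the boundary rebuilt from the plan's own reasoning, "Even if the remaining 50 intervention subjects to be enrolled experience no transfusions and the transfusion rate remains at 20% in the control group". The final control count is the interim count × 200/150, no further intervention events occur, and the trial stops if the final likelihood ratio p is ≥ 0.0492.

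Reading B reproduces the plan's figure of 26 at 30 control events: 40/200 against 26/200 gives p = 0.0585, and against 25/200 gives p = 0.0413. It also gives 21 at 25 control events and 32 at 35.

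**5. How likely is the trial to continue?** Exact binomial enumeration was used, with 150 per arm and all 300 outcomes known.

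| True rates, control vs TXA | Efficacy stop | Futility stop, A / B | Continue, A / B | Continue with p < 0.05 favouring TXA |
|---|---|---|---|---|
| 20% vs 10% | 0.367 | 0.002 / 0.053 | 0.631 / 0.580 | 0.327 |
| 20% vs 15% | 0.050 | 0.133 / 0.329 | 0.818 / 0.622 | 0.159 |
| 20% vs 20% | 0.005 | 0.447 / 0.729 | 0.547 / 0.266 | 0.023 |

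The last column is the same under A and B, so it does not depend on the missing figure.

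**The case against.** **Presence at the interim is not stated.** Section 10.2 gives his attendance a purpose, answering protocol questions, and describes the interim in a separate paragraph. It does not say at which meeting the interim is reviewed or that he sees data by arm. This stands, and it is why the finding is worded as possible exposure. But the section puts the interim under the committee whose meetings he attends. A rule about his vote on continuation makes most sense if he may be in the room when continuation is decided. His reason for attending does not limit what he hears.

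**Blinding is the plan's default.** Sections 5.6 and 9.1 could be read as covering him, and the bar on summary extracts shows some thought about aggregate leakage. That bar concerns database access by research staff. Section 5.6 concerns treatment assignment and does not name the principal investigator as such. Neither governs committee presentations.

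**The harm is limited.** This stands in part. The infusion bags are volume-matched, REDCap assigns after consent, and an aggregate result reveals no subject's arm. No section says that he controls transfusion orders. Relatedness judgements are also made without knowing the assignment. What remains is operational: equipoise, enrolment and practice common to both arms, none of which can be quantified from the documents.

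**The probabilities do not measure the harm.** Correct. They show how often the trial goes on after the look, not how often he sees the result or what follows if he does.

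**A recommendation to continue is itself informative.** Also correct: with the boundaries published in section 7.2, it says that neither was crossed. That is much less than the observed difference.

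**Conclusion.** The concern holds. As written, the plan lets the principal investigator learn the interim difference with up to 100 of 400 subjects (25%) still to enrol, and only his vote is restricted. If the design assumptions are right, the trial continues after the look with probability 58% to 63%. The probability that it continues with a nominally significant result (p < 0.05) favouring tranexamic acid is about one in three.

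This rests on even accrual, equal arms, all 300 outcomes being known at the interim, reading B (where used) applying at every control count, and the inference that he would be present for the interim. Confidence is therefore medium. No contradiction, wrong figure or direct differential bias is claimed; this is a design choice that should be changed because the protection is cheap.

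The figure of 100 concerns the formal interim only. Committee meetings begin at 50 subjects or 6 months. If safety data were shown by arm at a first meeting triggered by 50 subjects, which the documents do not state, 400 − 50 = 350 subjects would remain.

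**What to change.** In section 10.2, limit the principal investigator to an open session covering protocol questions and pooled data. Exclude him whenever data by arm are shown or discussed, and send him only the committee's recommendation to continue or stop.

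This takes one or two sentences and changes no sample size, power, endpoint or stopping boundary. It keeps the advisory role that section 10.2 gives him. The cost is that he is unavailable during the closed session, so the committee would have to put its protocol questions to him in the open session.

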11.1 Risk-Benefit Assessment

The study aims to provide data on the risks and benefits of TXA administration in the geriatric hip fracture population. While other studies have demonstrated benefit without significant complications when given in the orthopedic total joint population, there is not data from large studies conducted in the geriatric hip fracture population. The risks may be greater in this generally higher risk population, but the potential benefit also may be greater if the frequency of blood transfusion is greater. We therefore think the potential risk-benefit ratio is acceptable. The accuracy of this assumption will be assessed as the study is ongoing through safety monitoring and the interim analysis.

11.2 Process for Obtaining Informed Consent and HIPAA Authorization

All subjects will be provided a combined, written consent and HIPAA authorization form that describes the study in sufficient detail for subjects to make an informed decision about their participation in this study. This consent and authorization form will be submitted with the protocol for review and approval by the IRB. The formal consent and authorization of a subject, using the IRB-approved form, will be obtained before that subject undergoes any study procedure.

When obtaining consent and authorization, OAL physicians will discuss the study purpose, risks, benefits, and alternatives to participation and address questions and concerns with patients and their legally authorized representatives, when applicable. Research staff will be involved in the process of obtaining consent and authorization, by discussing with potential subjects the details of the study follow-up, how information about them will be used and disclosed, and who to contact in the case of injury or with questions or concerns. Given that the study is being conducted in the emergency hip fracture population, subjects or their representatives will not have extended time to review the written consent and authorization. Therefore, the physicians and research staff will take special care to ensure that subjects demonstrate understanding of the study in conversation. Subjects or their legally authorized representatives will be asked to sign the written consent and authorization form and will be given a copy of the form. After the consent and authorization process is complete, the OAL physician will document the process within the Epic subject medical record.

The OAL physician will make the determination as to whether a subject is medically or cognitively unable to give consent and authorization and who is appropriate to serve as the subject's legally authorized representative, following LG policies. The subject will be informed about the trial to the extent compatible with the subject's capacity for understanding. If the legally authorized representative is not available in person, the consenting physician may transmit the consent form to the representative electronically and discuss the study with the representative by phone. The legally authorized representative may return a signed copy by fax or email or in person prior to randomization. Alternatively, electronic signature may be obtained via the study database in REDCap.

For uses of a short form, an alteration of the HIPAA authorization requirement is requested. That is, in these circumstances, authorization to use and disclose health information will be obtained orally, but no signature will be obtained in the HIPAA authorization section of the consent form.

11.3 *Withdrawal of Consent or Revocation of Authorization*

Participation in TAHFT study is voluntary. Research subjects may withdraw, or their legally authorized representatives may withdraw them, from the study at any time during the course of the study. Refusing to participate or withdrawing from the research study will not impact a patient's medical care.

Unless a subject withdraws soon after consent and before surgery, it is likely that the study intervention will be completed. That is, when a subject withdraws from the study after surgery, s/he is withdrawing only from follow-up data collection from the medical record.

Some subjects or legally authorized representatives may wish to withdraw medical care. An OAL physician will review with them the standardized routine hip fracture follow up care for 90 days after surgery. If the subject or legally authorized representative desires to completely withdraw medical care, the OAL provider will document and monitor outcomes via phone calls or chart reviews. Also, if a subject relocates out of the Lancaster, PA, geographical area during the acute post-operative period, OAL will monitor subject outcomes via phone calls. Subjects will be asked if this information may be used in the research study.

Study data collection stops upon subject withdrawal from TAHFT study. For example, if subjects withdraw from the TAHFT study prior to surgery, operative and post-operative data will not be collected. Data that have already been collected up until study withdrawal will remain part of the TAHFT study database.

11.4 *Privacy and Confidentiality*

Patients will be approached about participating in the study in the emergency room, patient hospital room, or the pre-operative room. They will be extended as much privacy as possible, with conversations about the study occurring in the context of therapeutic decision-making. All follow-up interactions with participants also will occur in the context of medical care.

The use of subjects' medical data for research purposes will be explained in the consent and authorization process. The study database will contain the participants' names and medical record numbers to facilitate the conduct of the study. The study database will be accessible only to study personnel, as described in Section 9.1.

Identifiable data will not be disclosed outside of LG Health. However, subjects will be informed that their study data could be de-identified and shared with other researchers.

Data on hip fracture patients who do not participate in the TAHFT study will be recorded in a de-identified manner, to allow assessment of the generalizability of the patient population and study results.

12 *Study Finances*

12.1 *Funding Source*

Funding for this study will be financed through a grant from the von Hess Foundation.

12.2 *Conflict of Interest*

Research investigators and personnel are required to disclose any financial interests related to their job responsibilities on an annual basis. Financial interests are reviewed by the Research Compliance Committee as protocols are submitted and as they come up for continuing review. Any potential conflicts of interest must be managed to the satisfaction of the IRB to minimize influence on subject safety and study integrity.

12.3 *Subject Stipends or Payments*

The study participant will not incur additional costs from participating in this study. There are no programs to pay for medical care necessitated by adverse events associated with participation in this study. Payment for care for adverse events associated with TXA drug administration will be the responsibility of the subject or the subject's third party payer. Subjects will not receive any remuneration for participation.

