6.3.2 Follow Up Visits

The subject receives routine hip fracture post-operative care per the LGH geriatric fracture program. The post-hospital observational phase will include a minimum of two post-operative follow-up evaluations at two (2) weeks, six (6) weeks, and three (3) months.

The two (2) week, six (6) week, and three (3) month standard of care post hip surgery patient assessment will include evaluation of the following:

- X-rays to evaluate hip fracture and hardware placement
- Dressing check (2 week only)
- Physical therapy progress
- Weight bearing status
- Pain medication management
- Post-operative anti-coagulation management
- Bone density osteoporosis prevention conversation

The CRC conducts a medical chart review at the 6 week and 3 month time points for scheduled and unscheduled office visits a subject has with any provider for the following items:

- Subject assessment by the OAL provider
- Medication changes and updates
- Laboratory tests (if done)
- Hospital readmission and associated diagnosis in the interim since discharge after hip surgery
- Adverse events

If a subject reports visits or hospitalizations outside the LG system, study personnel will request permission to obtain data from the providers or health systems. If a subject is reported to be deceased during the follow-up period, the CRC will record this event in the study database.

6.4 *Unscheduled Visits*

It is anticipated that <5% of subjects require an additional unscheduled visit. Typically additional visits are to evaluate wound healing. Any relevant information from these visits will be captured by the medical chart reviews at 6 weeks and 3 months.

7 *Statistical Plan*

Statistical support will be provided by the Lancaster General Research Institute.

7.1 *Sample Size and Power Determination*

Power calculations are based on the assumptions that 20% of the control group will require transfusion as a result of the hip fracture and surgery, and that use of TXA will reduce that percentage by half to 10%. For 80% power with a two-sided alpha of 0.05, and using a likelihood ratio test, the sample size is calculated to be 200 per group with a 1:1 assignment ratio, or 400 total subjects.

[figure not shown]
7.2 *Statistical Methods*

For assessing the primary endpoint, we will calculate an odds ratio (with a 95% confidence interval) for transfusion with p-values calculated using a likelihood ratio.

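### Section 11.3 ends data collection at study withdrawal without asking whether passive record review may continue, so some randomised subjects can lose outcomes that sit in the hospital record

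*Combined protocol and SAP*

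**What the plan says.** Section 11.3 (Withdrawal of Consent or Revocation of Authorization) sets the rule: "Study data collection stops upon subject withdrawal from TAHFT study". It gives an example: "if subjects withdraw from the TAHFT study prior to surgery, operative and post-operative data will not be collected". The example makes no exception for subjects already randomised. The section then protects what is in hand: "Data that have already been collected up until study withdrawal will remain part of the TAHFT study database".

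The same section explains what withdrawal means once the operation is over: "when a subject withdraws from the study after surgery, s/he is withdrawing only from follow-up data collection from the medical record".

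Subjects who give up medical care altogether are treated separately. For them, "the OAL provider will document and monitor outcomes via phone calls or chart reviews". Subjects who move out of the area are followed by phone. The paragraph closes: "Subjects will be asked if this information may be used in the research study". No such question is described for a subject who withdraws from the study.

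The intervention is a single infusion before incision (sections 5.1 and 5.5), and study data come from Epic (section 3.3). Table 1 marks transfusions at the surgical period and at hospital discharge (days 2-4), and sections 6.2 and 6.3.1 describe the matching Epic reviews. After discharge, "The CRC conducts a medical chart review at the 6 week and 3 month time points" (section 6.3.2), looking back over visits, readmissions and adverse events.

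Section 7 gives no analysis population, no rule for missing primary outcomes and no allowance for withdrawal in the 400 subjects.

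**The concern.** Treatment is over before the first post-operative outcome can occur, and the outcomes accrue in a record that exists whether or not the subject stays in the study. Stopping abstraction at withdrawal therefore creates missing data after randomisation that could sometimes be avoided with the subject's permission.

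Two comparisons are exposed. The first is the primary comparison of transfusion among all randomised subjects. The second is the set of later outcomes (30-day readmission, 90-day complications and death), which carry the safety conclusion and include two of the items that section 10.2 lists for the monitoring committee. If subjects or families withdraw more often after a bad course, the missing outcomes are not a random sample. Nothing in section 7 says how the analysis would deal with that.

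**Working it through.** **1. What each withdrawal time puts at risk, reading sections 11.3, 6.2, 6.3 and Table 1 together**

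| Withdrawal | Primary outcome | Later outcomes |
|---|---|---|
| After randomisation, before surgery | Not collected, by the section 11.3 example | Not collected |
| After surgery, before the discharge abstraction (days 2-4) | Incomplete or missing; peri-operative transfusions may already be held under 6.2 | Not collected |
| After discharge abstraction, before the 6-week review (45 d ± 7 d) | Held | Events since discharge not yet abstracted; later events not collected |
| After the 6-week review, before the 3-month review (90 d ± 14 d) | Held | 30-day readmission held if the review was on schedule (earliest day 45 − 7 = 38); events not yet abstracted, and those still to come, at risk |

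Example for the third row: a readmission on day 20 followed by withdrawal on day 35. The event occurred while consent stood, but the review that would record it is due on day 38 at the earliest. Section 11.3 keeps what was collected and does not address what had occurred but was not yet abstracted.

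**2. The plan's sample size**

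Inputs (section 7.1): 20% v 10%, two-sided alpha 0.05, 80% power, likelihood ratio test, 1:1. The pooled normal formula gives

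n = [1.960·√(2·0.15·0.85) + 0.842·√(0.20·0.80 + 0.10·0.90)]² / 0.10² = (0.990 + 0.421)² / 0.01 ≈ 199 per group.

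The stated 200 per group is reproduced, and it leaves no margin for lost outcomes.

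**3. Loss unrelated to outcome**

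The test statistic is G = 2·Σ O·ln(O/E) over the four cells of the 2×2 table, rejecting when G > 3.841. Exact power is the sum of the product of the two binomial probabilities over all rejected tables. The documents give no withdrawal rate, so the loss below is an assumption, equal in both arms, and counts only subjects whose primary outcome is lost.

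| Primary outcomes lost | Per arm | Exact power, alpha 0.05 |
|---|---|---|
| 0% | 200 | 81.1% |
| 2% | 196 | 80.5% |
| 5% | 190 | 79.2% |
| 10% | 180 | 77.1% |

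At the final-analysis level of 0.0492 (section 7.2), the 2% and 5% rows become 80.2% and 78.8%. These are single-look figures.

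**4. Loss linked to outcome**

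Take the planned result, 40/200 v 20/200. G = 2·[40·ln(40/30) + 160·ln(160/170) + 20·ln(20/30) + 180·ln(180/170)] = 7.97, p = 0.0047.

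- Remove 4 transfused control subjects: 36/196 v 20/200, G = 5.77, p = 0.016.
- Remove 8 (8/400 = 2% of all subjects): 32/192 v 20/200, G = 3.81, p = 0.051, above 0.0492.

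This is an illustrative extreme, since every lost subject is a transfused control. It shows that the pattern of loss matters more than the amount: 2% lost at random costs about 0.6 points of power, while 2% lost in this pattern reverses the conclusion.

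**The case against.** The strongest reply is that section 11.3 describes post-surgery withdrawal as withdrawal from record review itself. Visits are standard care, so a subject content with chart review has little reason to withdraw, and few would accept an offer to continue it. The section also covers revocation of authorization, after which the coordinator may have no right to open the record. Both points stand in part. They limit how much data the question would recover, and they mean that refusal and revocation must end collection. They do not show that nobody would agree, and the plan does not ask.

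The exposure is also narrow. Randomisation falls just before surgery, so the interval before incision is short, and the primary outcome is in hand after the discharge abstraction. Subjects and clinical staff are blinded, which makes withdrawal that differs by arm less likely. These points stand and hold the size down.

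Three stronger readings are tempting, and the documents do not support them:

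- A reader might infer that events before withdrawal are discarded. Section 11.3 keeps data already collected and is silent on earlier events not yet abstracted.
- A reader might infer that a day-1 withdrawal leaves no transfusion status. Section 6.2 and Table 1 also collect transfusions in the surgical period, so the status would be incomplete and not necessarily absent.
- A reader might call the section inconsistent because those who leave care or relocate are asked a permission question. They have not withdrawn from the study, so a different rule is defensible. Their paragraph shows only that such a question is already in use.

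Finally, the consent and authorization form is not part of the public document and may address continued record review. The point is about the protocol text.

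**Conclusion.** The point holds as a cheap improvement. Section 11.3 states a rule under which some randomised subjects lose outcomes that could be read from Epic with their permission, and it leaves open whether earlier events not yet abstracted may be recorded.

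If the loss is random and equal between arms, the effect on the primary analysis is small: about 0.6, 1.9 and 4.0 points of power at 2%, 5% and 10% loss. All three rates are assumptions, and they apply only to withdrawals early enough to cost the primary outcome. The case therefore rests on the possibility of outcome-linked loss, which the documents neither quantify nor rule out, and on the later safety outcomes, which stay exposed for longer. A reader might want a count of safety events lost. The documents give neither a withdrawal rate nor event rates from which to derive one.

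**What to change.** Amend section 11.3 and the matching consent and authorization text:

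1. Ask each withdrawing subject or representative whether passive chart review for transfusion, readmission, complications and death may continue to day 90. Collection stops only if this is refused or authorization is revoked.
2. State that Epic events dated up to the day of withdrawal may be abstracted where the signed authorization allows it, whether or not a scheduled review has taken place.
3. Limit the pre-surgery example to subjects not yet randomised, or who refuse.
4. Record the type and date of each withdrawal and report them by arm.

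The cost is IRB review of the wording and one extra question at withdrawal. No visit or test is added. Some subjects will still refuse, so a little missing data will remain.
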